5.6 Health Care Utilization

Participants will be asked to report health care utilization including: telephone calls to the medical provider for medical advice, e-mail portal, electronic health record, clinic visits, urgent care visits, emergency department visits and hospital admissions occurring through day 43 according to the schedule in Table 1 above. The reason for health care use will also be obtained. Electronic or paper health records will be obtained and reviewed to confirm reports of clinic visits, urgent care visits, emergency department visits and hospital admissions. Health care utilization and the reason for health care utilization will be recorded on the symptom diary.

5.7 Biospecimens Collection & Handling

5.7.1 Serum

Blood specimens will be collected during study visits as described in Table 1. All blood samples (≈10 mL) will be collected into serum separator tubes and processed as follows:

- Allow blood to clot at room temperature for at least 30 minutes while standing upright in a rack.
- Centrifuge tube within 8 hours of collection at 1100 to 1300 RCF(g) for 10 minutes.
 - Gently remove the vacutainer stopper avoiding serum contamination with red blood cells. Using a single-use pipette, transfer 1.0 mL aliquots of serum (top layer) into 1.0mL or 1.8 mL cryovials, up to 5 cryovials are expected. If less than 1 mL of processed serum is collected, it is a protocol deviation

- All cryovial aliquots will be barcode labelled and contain a unique identifier via REDCap. Numbers should be placed lengthwise on the tube.
- Freeze the cryovials at -80°C in the temperature-monitored research center freezer for future shipment.
- Serum aliquots will be stored in the Duke Human Vaccine Institute Accessioning Lab, the Boston at the Maxwell Finland Laboratory for Infectious Diseases, and at Cincinnati Children's Hospital until planned HAI analyses at which point the samples stored at BMC and Cincinnati will be shipped to Duke where all HAI analyses will be done

6 LABORATORY ANALYSES

6.1 Influenza Hemagglutination Inhibition (HAI) Assay

Influenza Hemagglutination Inhibition (HAI) Assays will be performed on sera collected, contingent on additional funding. Briefly, reference wild-type, reassortant, or vaccine virus strains representative of the specific viral antigens included in the 2017-2018 and 2018-2019 influenza vaccine will be used to evaluate the relative levels of all three influenza strain-specific antibodies in participant serum samples collected pre- and 28 days post-vaccination from all study participants and at 181 days post-vaccination in a subset of 100 participants at Duke. To accomplish these activities all participant samples will be interrogated for influenza antibodies against the strains of interest using the influenza hemagglutination inhibition assay (HI). This assay is considered the “gold-standard” measure by which to evaluate seroconversion/seroprotection in response to seasonal influenza vaccination. This assay will be performed in accordance with the Duke Regional Biocontainment Laboratory Virology Unit's fully optimized and approved SOP (RVUSOP004 Influenza HI of Serum Samples). Briefly, test samples will be assayed by HAI as duplicate 2-fold dilution series starting at 1:10. Serum dilutions are then incubated with a concentration of virus verified to possess a known potential for red blood cell (RBC) agglutination. The presence of virus-specific antibodies is visualized via incubation of the virus-serum mixture with a RBC solution; the endpoint titer for a given dilution series is then expressed as the reciprocal of the final dilution in which complete HAI is observed. By convention, seronegative samples are defined as having an endpoint HAI titer < 40 and seropositive samples as having an endpoint titer of $\geq 1:40$; and seroconversion as a 4-fold change in endpoint titer relative to pre-immunization baseline or a change from <10 to $\geq 1:40$ ³⁷.

7 STATISTICAL CONSIDERATIONS

In collaboration with the Boston Medical Center and Cincinnati sites, the research team at Duke will oversee the statistical analysis. Data will reside on a secure Duke server maintained by Duke Health Technology Solutions (DHTS). For the study, a database will be developed and a data set for the study without personal identifiers will be made available to the CDC upon request. Duke statisticians will develop a comprehensive Statistical Analysis Plan. The summary points of the analysis plan are presented below.

7.1 Analysis Plan

Should an interim safety analysis be required, the alpha level will be adjusted to assure the overall type I error is maintained at the one-sided alpha 0.025 level for the primary outcome of non-inferiority.

7.1.1 Sample Size

Safety: Based on data from prelicensure studies^{4,5,7}, we assume that 5% of older adults have moderate/severe injection-site reactions after aIIV3 or IIV3-HD. We have selected a clinically meaningful non-inferiority margin of 5%. Statistical calculations, without consideration of drop-out, show that with an alpha of 0.025 (one-sided), we would need 668 total subjects (334 subjects in each group across all study sites) to have at least 80% power be able to demonstrate that the proportion of moderate/severe pain was non-inferior after aIIV3 vs. IIV3-HD. Enrollment in this study shall occur during two influenza seasons (2017-18 and 2018-19).

Immunogenicity: Based on data from prelicensure studies^{4,5,7}, we conservatively estimate that 50% of older adults demonstrate seroconversion after vaccination with aIIV3 or IIV3-HD for the H3N2 strain. We have selected a clinically meaningful non-inferiority margin of 10%. Statistical calculations, without consider of drop-out, show that with an alpha of 0.025 (one-sided), we would need 780 total subjects (390 subjects in each group across all study sites) to have approximately 80% power to able to demonstrate that the seroconversion rate after aIIV3 was non-inferior to IIV3-HD.

The total number of subjects needed for this study was derived based on 4 factors: 1) Sample size needed for adequate statistical power to test the safety hypothesis; 2) sample size needed for adequate statistical power to test the immunogenicity hypothesis; 3) potential for subject drop-out; and 4) feasibility of dividing subjects across 2 sites. Based on these considerations, the study aims to enroll at least 880 subjects to assess both the safety and immunogenicity endpoints. The study aims to enroll at least 720 to test only the safety hypothesis.

7.1.2 Analysis Populations

Full Analysis Population:

- For Primary Objective 1 and Secondary Objective 1, the primary analysis population will be the Full Analysis Population; defined as all subjects who are randomized, vaccinated, and provide at least one day of complete data on the symptom diary.
- For Primary Objective 2 and Secondary Objective 2, the primary analysis population will be the Full Analysis Population; defined as all subjects who are randomized and vaccinated.

Immunogenicity Population:

For Primary Objective 3 and Secondary Objective 3 the primary analysis will be for the Immunogenicity Population; defined as subjects who received vaccine, provide baseline and Visit 4 blood draws of acceptable volume and quality within the protocol-defined time frame with

no protocol violations affecting immunogenicity. Protocol violations affecting the immunogenicity analyses will be defined in the Statistical Analysis Plan (SAP).

The Full Analysis Population is the primary population for analysis unless otherwise stated.

7.1.3 Primary Objective 1

- To compare the proportions of moderate/severe injection site pain after aIIV3 and IIV3-HD in the full study population
 - Hypothesis: the proportion of subjects who have moderate/severe injection site pain within the first week post-vaccination will be non-inferior for aIIV3 compared to IIV3-HD in the full study population

This objective will be assessed using a one-sided non-inferiority test with the alpha level set at 0.025 and non-inferiority margin of 5%.

The null hypothesis is aIIV3 is inferior to IIV3-HD in regards to the proportion of subjects having moderate or severe injection site pain in the first week post vaccination.

$$H_0: aIIV3 - IIV3-HD \geq 0.05 \text{ (5\%)}$$

The alternative hypothesis is aIIV3 is non-inferior to IIV3-HD in regards to the proportion of subjects having moderate or severe injection site pain in the first week post vaccination.

$$H_a: aIIV3 - IIV3-HD < 0.05 \text{ (5\%)}$$

The upper bound of the one-sided binomial confidence interval of the difference will be used to make this assessment.

7.1.4 Primary Objective 2

- To compare serious adverse events and events of clinical interest after aIIV3 and IIV3-HD in the full study population and by age-group

The proportion and 95% exact binomial confidence interval of serious adverse events and events of clinical interest, as well as the total number of events, will be presented by site, vaccine group, severity, and relatedness. Listings of the serious adverse events will also be presented. This information will also be prepared for the subset ($N \geq 176$) of subjects 80 or older.

7.1.5 Primary Objective 3

- To compare the seroconversion rate for the H3N2 influenza A strain after aIIV3 and IIV3-HD in the full study population
 - Hypothesis: the seroconversion rate for the H3N2 influenza A strain in the full study population after aIIV3 will be non-inferior to IIV3-HD

This objective will be assessed using a one-sided non-inferiority test with the alpha level set at 0.025 and non-inferiority margin of 10%.

The null hypothesis is the allV3 H3N2 seroconversion rate is inferior to IIV3-HD seroconversion rate.

$$H_0: \text{allV3 H3N2 rate} - \text{IIV3-HD H3N2 rate} \geq 0.1 \text{ (10\%)}$$

The alternative hypothesis is the allV3 H3N2 seroconversion rate is non-inferior to IIV3-HD H3N2 seroconversion rate.

$$H_a: \text{allV3 H3N2 rate} - \text{IIV3-HD H3N2 rate} < 0.1 \text{ (10\%)}$$

The upper bound of the one-sided binomial confidence interval of the difference will be used to make this assessment.

7.1.6 Secondary Objective 1

- To compare the proportions of local and systemic reactions after allV3 and IIV3-HD in the full study population and by age-group (65-79 years and ≥ 80 years) (other than moderate/severe injection site pain in the full study population)

The proportions in the full study population will be conducted as for Primary Objective 1 using a non-inferiority test to determine if allV3 is non-inferior to IIV3-HD with a 5% non-inferiority margin. These secondary objectives will be conducted with a one-sided alpha at the 0.01 level to adjust for multiple comparisons. It is recognized that with 12 different assessments at the alpha 0.01 level (given the events are truly independent) we are allowing an 11.4% chance of making a type I error.

The age-group assessments will be assessed using standard two-sided 95% confidence boundaries of the difference in proportions between the groups. No formal statistical testing will be implemented for the age-group comparisons.

7.1.7 Secondary Objective 2

- To describe and compare changes in health-related quality of life after allV3 and IIV3-HD in the full study population and by age-group

Each HRQOL instrument produces a summary score to measure health-related quality of life. The change in score from pre-vaccination (baseline, Visit 1) to post-vaccination (Day 3, Visit 2) time points will be compared within and between the two groups.

The Late-Life Disability and Function Instrument and Late-Life Disability and Function Instrument-Computer Adapted Test (Year 1 Only)

The function and disability sections scale raw scores are transformed to a 0 (worst health) to 100 (best health) scale. The changes from baseline will be assessed within vaccine group using a paired t-test for the function and disability outcomes. If normality assumptions are not met, the testing will be performed with a Wilcoxon signed-rank test. The Mann-Whitney U test (Wilcoxon rank-sum test) will be used to compare the difference scores from baseline between the two vaccine groups for the function and disability outcomes.

EQ-5D-5L and Visual Analogue Scale (VAS)

The EQ-5D-5L responses are converted to a Utility Index that ranges from -0.109 (worst health) to 1.0 (best health) using the US specific value sets (http://www.euroqol.org/fileadmin/user_upload/Documenten/Excel/Crosswalk_5L/EQ-5D-5L_Crosswalk_Value_Sets.xls). The EQ VAS has a range of 0 (worst health) to 100 (best health). The changes from baseline will be assessed within vaccine group using a paired t-test for the index values and VAS. If normality assumptions are not met, the testing will be performed with a Wilcoxon signed-rank test. The Mann-Whitney U test (Wilcoxon rank-sum test) will be used to compare the difference scores from baseline between the two vaccine groups for the index values and VAS.

These health-related quality objectives will be conducted with a two-sided alpha at the 0.01 level to adjust for multiple comparisons. It is recognized that with 12 different assessments at the alpha 0.01 level (given the events are truly independent) we are allowing a 11.4% chance of making a type I error.

The statistical tests described above will also be performed for the subset (N=176) of subjects 80 or older. This testing will be considered exploratory with an alpha level of 0.05 with no alpha adjustment.

7.1.8 Secondary Objective 3

To compare serum hemagglutination inhibition (HAI) antibody titers after aIIV3 and IIV3-HD for each of the three influenza vaccine strains contained in the respective vaccine for that season in the full study population and by age-group (except for seroconversion for the H3N2 strain in the full study population)

Responses to each influenza antigen will be analyzed, with the exception of seroconversion for H3N2, which is analyzed in Primary Objective 1. The proportion of subjects with seroprotection (pre- and post-immunization) seroconversion (4-fold rise from baseline) in the two treatment groups will be presented along with 95% exact binomial confidence intervals. A 95% confidence interval of the difference in proportions between the treatment groups will also be presented.

The GMTs for each influenza antigen, including H3N2, and 95% confidence boundaries will be presented for both treatment groups. A 95% confidence interval of the difference in GMTs between the treatment groups will also be presented. This information will also be prepared for the subset (N≥176) of subjects 80 or older.

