1.2 Summary and Rationale

The safety profile or immunogenicity of aIIV3 and IIV3-HD have not been compared head-to-head. The decision of which vaccine to use in older adults will be enhanced by a better understanding of the safety and immunogenicity of these vaccines, as well as the relative impact on health-related quality of life, functioning and participant perspectives of the vaccination experience. Furthermore, the best method for collecting information on health-related quality of life, functional status and other non-medically attended adverse events after moderate to severe injection site or systemic reactions is not known. This study will address this gap in knowledge in older adults after vaccination. This study will also add value to pandemic influenza preparedness by providing data on risks and benefits of influenza vaccination in older adults that are not currently available.

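### Primary Objectives 1 and 3 stop at a one-sided non-inferiority bound; a two-sided interval and a pre-specified superiority step would add a conclusion at no cost in sample size or alpha

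*Combined protocol and SAP*

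**What the plan says.** Section 1.2 gives the purpose of the trial: "The decision of which vaccine to use in older adults will be enhanced by a better understanding of the safety" and immunogenicity of the two vaccines. Primary Objective 1 is introduced in 7.1.3 as "To compare the proportions of moderate/severe injection site pain after aIIV3 and IIV3-HD in the full study population". The hypothesis beneath it is that the proportion with pain "will be non-inferior for aIIV3 compared to IIV3-HD in the full study population". The test is: "This objective will be assessed using a one-sided non-inferiority test with the alpha level set at 0.025 and non-inferiority margin of 5" percentage points. The decision rule is: "The upper bound of the one-sided binomial confidence interval of the difference will be used to make this assessment".

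Section 7.1.5 follows the same pattern for Primary Objective 3, H3N2 seroconversion: "This objective will be assessed using a one-sided non-inferiority test with the alpha level set at 0.025 and non-inferiority margin of 10" percentage points. It is again judged by the upper bound of aIIV3 minus IIV3-HD, with a null hypothesis that this difference is at least +0.1.

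Primary Objective 2 (section 7.1.4) is different. It is descriptive, with exact 95% intervals for each group and no non-inferiority test, and the point does not concern it.

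Elsewhere the plan does use two-sided intervals of the difference. Section 7.1.6 plans two-sided 95% limits for reactions by age group. Section 7.1.8 plans a 95% interval of the difference for seroprotection and seroconversion, but excepts H3N2 seroconversion because it is a primary endpoint. Section 7 describes itself as the summary points of a fuller SAP still to be developed.

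**The concern.** The trial is meant to inform a choice between two licensed vaccines. For that purpose the reader needs the size and direction of the difference, with both limits. For the two endpoints that carry the formal hypotheses, the plan produces one bound and one yes/no answer in the full population. As 7.1.6 is worded, pain within each age group gets a two-sided interval and pain in the full population does not. Seroconversion for H1N1 and B gets one and H3N2 in the full population does not.

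Two things are lost. If aIIV3 turns out better, no superiority claim has been pre-specified, so the result could be described but would not count as confirmatory. If aIIV3 causes more pain within the margin, showing this needs a lower limit, which is not planned.

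**Working it through.** **Inputs.** From 7.1.1: pain, "we assume that 5% of older adults have moderate/severe injection-site reactions after aIIV3 or IIV3-HD", margin 5 points; H3N2 seroconversion 50% in both arms, margin 10 points; one-sided alpha 0.025; enrolment of at least 880. Allocation is 1:1 (5.2.1), so 440 per arm without drop-out. The 390 per arm is the plan's requirement for seroconversion.

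**1. The plan's own sample sizes.** Farrington-Manning score test: n per arm = ((1.96·s0 + 0.8416·s1)/margin)², where s0 uses the rates fitted under the null and s1 the assumed rates.
- Pain: null rates 8.49% and 3.49%, s0 = 0.3337, s1 = √(2·0.05·0.95) = 0.3082. n = ((0.6540 + 0.2594)/0.05)² = 333.7, so 334. This matches the statement that "we would need 668 total subjects (334 subjects in each group across all study sites) to have at least 80% power".
- Seroconversion: null rates 55% and 45%, s0 = 0.7036, s1 = 0.7071. n = ((1.3790 + 0.5951)/0.10)² = 389.7, so 390. This matches the plan's 780 in total.

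The trial is sized for non-inferiority and the sizes are right.

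**2. Alpha.** The upper limit of a two-sided 95% interval is the one-sided 97.5% bound already planned for pain. Superiority is tested only if non-inferiority has been shown, and rejecting superiority's null implies rejecting the non-inferiority null. Within each objective the one-sided error therefore stays at 0.025, and 334 and 390 per arm stand.

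**3. Power of the superiority step.** Power = Φ((|p1 − p2|·√n − 1.96·√(2·p̄(1 − p̄))) / √(p1(1 − p1) + p2(1 − p2))).
- Pain 5% vs 2%, n = 440: (0.6293 − 0.5094)/0.2590 = 0.463, power 68%. For 5% vs 1%: 94%.
- Seroconversion 50% vs 60%, n = 390: (1.9748 − 1.3790)/0.7000 = 0.851, power 80%.

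**4. How the pain interval would read.** Wald 95% limits, 440 per arm, 22/440 (5%) on IIV3-HD:

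| aIIV3 | Difference (points) | 95% interval | Reading |
|---|---|---|---|
| 10/440 | −2.73 | −5.19 to −0.26 | better |
| 30/440 | +1.82 | −1.30 to +4.93 | non-inferior (largest such count) |
| 37/440 | +3.41 | +0.11 to +6.71 | worse (smallest such count), not non-inferior |

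At a 5% control rate no result is both non-inferior and worse. At low rates it can happen: 18/440 vs 7/440 gives +2.50 points (0.31 to 4.69), and 20/440 vs 9/440 gives +2.50 (0.15 to 4.85). With 11 control events (2.5%) or more, up to the assumed 5%, no count does both.

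**5. Direction of Objective 3.** With 390 per arm and 50% on IIV3-HD, the probability of declaring non-inferiority is:

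| True aIIV3 − IIV3-HD | As written (upper bound < +10) | Lower limit > −10 |
|---|---|---|
| −15 points | about 1.00 | about 0.00 |
| 0 | 0.80 | 0.80 |
| +15 points | about 0.00 | about 1.00 |

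A superiority step cannot be attached to the rule as written. The interval's half-width is 1.96·√(0.5/390) = 7.0 points. Under the corrected rule non-inferiority needs an observed difference above about −3.0, and significantly worse needs one below −7.0, so the two cannot coincide near 50%.

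**The case against.** The best defence is that nothing here is wrong. Each objective to compare carries its own non-inferiority hypothesis, the test answers it, and the sample size was derived for it. Omitting an optional superiority step does not invalidate the primary conclusion. That stands, and it makes this an improvement rather than a correction.

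A reader might also infer that a clearly better or clearly worse result could not be stated at all. The documents do not support that.
- For pain, the planned upper bound already shows a better result when it falls below 0. With 9/440 vs 22/440 it is −0.53 points. What is missing is the pre-specified claim.
- Nothing in 7.1.3 or 7.1.5 bars reporting the rates or the difference.
- Non-inferior but significantly more pain needs a control rate of about 1–2%, against the assumed 5% and the 4.2% and 4% cited in section 1.1. With 440 per arm its probability is about 0.4% at true rates of 4.2% vs 4%, and about 0.03% at 5% vs 5%.
- The gain depends on a real difference. At 4.2% vs 4% the chance of an upper bound below 0 is about 1.7%.

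Finally, the announced comprehensive SAP may contain the missing wording. It is not in the supplied text, so this is unknown.

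**Conclusion.** The point holds for Primary Objectives 1 and 3 only. In the full population, section 7 plans a single one-sided bound for each, without a two-sided interval of the difference or a superiority step, and so gives these endpoints less than their age-group and other-strain counterparts. The main value of the change is a confirmable claim of superiority, with about 68% power for pain at 5% vs 2% and about 80% for seroconversion at 50% vs 60%. The ability to flag more pain within the margin is a minor gain. The figures assume equal arms of 440 (no drop-out) for pain and 390 for seroconversion, and Wald limits for the interval readings; the alternative rates are illustrations, not expectations in the plan. The reversed direction in 7.1.5 is the more serious fault and comes first.

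**What to change.** 1. In 7.1.5, restate the null hypothesis as aIIV3 minus IIV3-HD ≤ −10 points and the alternative as > −10 points, judged by the lower limit.
2. In 7.1.3 and 7.1.5, report the two-sided 95% interval of aIIV3 minus IIV3-HD in the full population, with the interval method named and the same method used for both steps.
3. Pre-specify that, once non-inferiority is met, superiority of aIIV3 is tested from the same interval at one-sided 0.025. For pain, non-inferiority requires the upper limit below +5 points and superiority the upper limit below 0. For H3N2 seroconversion, non-inferiority requires the lower limit above −10 points and superiority the lower limit above 0. If section 7.1's interim adjustment changes alpha, both steps use the adjusted level.
4. State that a pain interval inside the margin but wholly above 0 is reported as such, alongside the non-inferiority conclusion.

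The cost is wording in the protocol and SAP, fixed before unblinding. No further subjects, data or alpha are needed.

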2.2 Study Outcome Measures

Where possible, all outcome measures will be evaluated and compared between the two treatment groups for the full population and in both age subsets (65-79 years and ≥ 80 years)

2.2.1 Primary Outcome Measures:

1. Comparison of the proportion of subjects reporting moderate/severe injection site pain within the first week post-vaccination in both treatment groups.
2. The frequency and descriptions of serious adverse events and adverse events of clinical interest observed in the two treatment groups.

3. H3N2 HAI seroconversion: The proportion of subjects achieving H3N2 seroconversion at day 29 (an HAI titer \geq 1:40 at day 29 if the baseline titer is $<$ 1:10 or a minimum four-fold rise in HAI titer if the baseline titer is \geq 1:10) in the respective season's vaccine.

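### Primary Objective 2 is to compare SAEs and events of clinical interest between the vaccines, but 7.1.4 plans no interval for the between-arm difference and names age-specific output only for those 80 or older

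*Combined protocol and SAP*

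**What the plan says.** Section 7.1.4 states the aim as "To compare serious adverse events and events of clinical interest after" the two vaccines, in the full population and by age group. The matching outcome measure in 2.2.1 is descriptive: "The frequency and descriptions of serious adverse events and adverse events of clinical interest observed in the two treatment groups". Section 2.2 opens with a general commitment: "Where possible, all outcome measures will be evaluated and compared between the two treatment groups for the full population and in both age subsets", and names the subsets as 65–79 and 80 or older. The Protocol Summary also says these events will be compared between the groups through 42 days after vaccination.

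The analysis text in 7.1.4 is short. It offers "The proportion and 95% exact binomial confidence interval of serious adverse events and events of clinical interest", plus total event counts, broken down by site, vaccine group, severity and relatedness, and listings of the SAEs. It then adds "This information will also be prepared for the subset" of those 80 or older (at least 176). It names no difference, ratio, interval for a difference or test, and no output for ages 65–79.

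Section 7 introduces itself as a summary of a comprehensive SAP that is still to be developed.

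**The concern.** An exact binomial interval describes one proportion in one arm. It says nothing direct about the contrast between arms, which is what the objective is about. If 7.1.4 is followed as written, a primary safety objective worded as a comparison yields no estimate of the difference with its uncertainty.

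This matters because the stated rationale for the trial is that the two vaccines have not been compared head-to-head. For uncommon serious events, the useful statement is how large a difference the data can rule out. Two separate intervals do not give it. A reader who looks at whether they overlap is applying a much stricter criterion than a 95% interval for the difference, and can miss a difference that the data do show.

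The age-group gap is secondary. By-age comparison is part of the objective, but only the older stratum is listed, and that is the smaller and less precise of the two.

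**Working it through.** **1. Other objectives in section 7**

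| Section | Objective | Between-arm inference planned | Age-specific output named |
|---|---|---|---|
| 7.1.3 | Primary 1 | Non-inferiority test, interval of the difference | None (full population only) |
| 7.1.4 | Primary 2 | None | 80 or older only |
| 7.1.5 | Primary 3 | Non-inferiority test, interval of the difference | None (full population only) |
| 7.1.6 | Secondary 1 | Non-inferiority tests; by age, "The age-group assessments will be assessed using standard two-sided 95% confidence boundaries of the difference in proportions between the groups", with no formal testing | Both age groups |
| 7.1.7 | Secondary 2 | Mann-Whitney test between arms | "The statistical tests described above will also be performed for the subset (N=176) of subjects 80 or older" |
| 7.1.8 | Secondary 3 | Per-arm exact intervals, and then "A 95% confidence interval of the difference in proportions between the treatment groups will also be presented" | 80 or older only |

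Two things follow. Section 7.1.8 treats per-arm exact intervals and the interval of the difference as separate outputs, so the first cannot be read as implying the second. Section 7.1.6 already uses intervals of a difference without a test, so the format is familiar in this plan. The missing 65–79 output is a pattern shared with 7.1.7 and 7.1.8. The missing interval for the difference is specific to 7.1.4.

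**2. Inputs**

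The only figure in 7.1.4 is the size of the older subset, and it reproduces: 0.20 × 880 = 176, and 704 + 176 = 880 (5.2.1). Equal allocation, which I also assume in the older stratum, gives 880/2 = 440, 704/2 = 352 and 176/2 = 88 per arm. I take each proportion as subjects with at least one event. The documents give no SAE rate, so all counts and risks below are assumptions.

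**3. Per-arm intervals against an interval for the difference**

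- Exact (Clopper-Pearson) limits for x of n are the 2.5% point of Beta(x, n−x+1) and the 97.5% point of Beta(x+1, n−x). For 9/440 this gives 0.94–3.85%; for 20/440, 2.80–6.93%. The intervals overlap.
- The Miettinen-Nurminen interval contains all d with |z(d)| ≤ 1.96, where z(d) = (p̂₁ − p̂₂ − d) / √{[p̃₁(1−p̃₁)/n₁ + p̃₂(1−p̃₂)/n₂] × N/(N−1)}, N = n₁ + n₂, and p̃ are the maximum-likelihood estimates under p₁ − p₂ = d.
- At d = 0, p̃ = 29/880 = 0.03295 and the observed difference is 11/440 = 0.0250. The standard error is √(0.03295 × 0.96705 × 2/440 × 880/879) = 0.01204, so z = 2.08, above 1.96. Zero is excluded.
- Solving for both limits gives +0.15 to +5.09 percentage points.

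**4. How often the two readings disagree**

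This enumerates all binomial outcomes with 440 per arm.

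| True risks | Interval of difference excludes 0 | Exact intervals disjoint |
|---|---|---|
| 2% v 2% | 4.8% | 0.2% |
| 2% v 3% | 15.6% | 1.9% |
| 2% v 4% | 41.6% | 10.7% |
| 2% v 5% | 69.1% | 30.6% |

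**5. Precision the added interval would have**

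Half-widths of the Miettinen-Nurminen 95% interval with equal counts in both arms:

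| Population | Per arm | No events | Events per arm | Half-width (points) |
|---|---|---|---|---|
| All | 440 | 0.87 | 4, 9, 13, 18 | 1.51, 2.04, 2.38, 2.73 |
| 65–79 | 352 | 1.08 | 4, 7, 11, 14 | 1.89, 2.31, 2.76, 3.05 |
| 80 or older | 88 | 4.21 | 1, 2, 3, 4 | 5.15, 5.93, 6.61, 7.20 |

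The no-event limit has a closed form, z²c/(n + z²c) with c = N/(N−1). For n = 440 it is 3.846/443.846 = 0.87%; for n = 88, 3.863/91.863 = 4.21%. A simple normal-approximation interval would have zero width here, so the method needs naming in advance. Newcombe's interval is close to Miettinen-Nurminen at these counts (for example 5.11 against 5.15 points for one event per arm of 88).

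**The case against.** The strongest reply is that 7.1.4 delivers what the outcome measure promises. That measure asks for frequencies and descriptions. Objective 2, unlike Objectives 1 and 3, has no hypothesis, margin or power basis, and a table by vaccine group is a descriptive comparison. This stands to the extent that no test is required. It does not explain why the objective says compare while the analysis gives no measure of the contrast with its uncertainty.

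Second, little information is lost. The point difference follows by subtraction, the 65–79 counts follow from the overall and 80-or-older counts, and a reader with counts and denominators could compute an interval. That is true. What is lost is prespecification of the effect measure and method.

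Third, section 7 is a summary, and the later SAP may include the interval. That SAP is not in the documents, so the finding is about the wording of 7.1.4, and the SAP can close it.

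Fourth, the disagreement in step 4 depends on the assumed effect. Section 1.1 says SAE proportions appear similar across the vaccines. At equal true risks, nearly all the disagreement is chance exclusion of zero; it becomes large only at about a doubling of risk. The documents also set no overlap rule. This is fair: the figures show that per-arm intervals are a poor substitute, not that a difference is expected. For the rarest events of clinical interest, such as anaphylaxis, the no-event row may apply and the interval then largely restates the sample size.

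Fifth, section 2.2 already commits to both age subsets where possible. So the 65–79 omission is a failure to carry that through and is the lesser part of the point.

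**Conclusion.** The point holds. As written, 7.1.4 gives no estimate with uncertainty for the comparison that Primary Objective 2 names, and it is the only primary or secondary objective in section 7 without between-arm inference. The omission of ages 65–79 is real but minor, since two other sections share it and the counts can be recovered.

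The size is moderate. No conclusion is made wrong and no data are lost, but a primary safety result would be reported without a prespecified statement of how large a difference the trial excludes. At assumed risks of about 1–4% per arm, that statement would be informative overall (about ±1.5 to ±2.7 points) and in those aged 65–79 (about ±1.9 to ±3.1), and weak in those 80 or older (about ±5 to ±7). These figures rest on equal allocation at the minimum planned enrolment, all enrolled subjects being vaccinated, and event rates that the documents do not supply. The finding about the text depends on none of them. It should be corrected.

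**What to change.** In 7.1.4, or in the SAP that section 7 announces, add the risk difference (aIIV3 minus IIV3-HD) in the proportion of subjects with at least one SAE, and the same for events of clinical interest. Give each a two-sided 95% interval by a named method suited to sparse data (Miettinen-Nurminen or exact unconditional), for the full population, ages 65–79 and ages 80 or older. State that these are estimates without a formal test. Keep the planned per-arm exact intervals, counts and listings. Optionally, repeat in 7.1.4 the 42-day comparison window given in the Protocol Summary.

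The cost is a few sentences and one table, with no new data and no change to sample size or error control. The drawback is wide intervals for rare events, mainly in those 80 or older, where even with no events in either arm the interval reaches about 4 points each way. The text should say in advance that an interval including zero in that stratum is not evidence of equal risk.
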